3.6.6. Vital Signs and ECG Parameters

3.6.6.1. Vital Signs

Vital signs for each visit during the entire study will be summarized by enrollment group and overall. All vital signs data will be presented in the subject data listings.

Number and percentage of subjects with vital sign values considered PCS occurring at any post-baseline visit will be summarized by enrollment group and overall. Criteria for PCS are presented in [Table 3](#) and will be presented for each criterion. The percentages will be calculated relative to the number of subjects with non-PCS baseline values with respect to the specific criterion and at least 1 post-baseline assessment. A supportive listing will present all values for a parameter for subjects with at least one PCS value for that parameter.

In addition, the figure of mean change from baseline along with the corresponding SE will be summarized by visit and enrollment group, and overall for systolic blood pressure, diastolic blood pressure, and pulse rate.

Table 3: Criteria for Potentially Clinically Significant (PCS) Vital Signs

Parameter	Criteria
Systolic Blood Pressure	Low: $\leq 90 \text{ mm Hg}$ and decrease $\geq 20 \text{ mm Hg}$ High: $\geq 180 \text{ mm Hg}$ and increase $\geq 20 \text{ mm Hg}$
Diastolic Blood Pressure	Low: $\leq 50 \text{ mm Hg}$ and decrease $\geq 15 \text{ mm Hg}$ High: $\geq 105 \text{ mm Hg}$ and increase $\geq 15 \text{ mm Hg}$
Pulse Rate	Low: $\leq 50 \text{ mm bpm}$ and decrease $\geq 15 \text{ bpm}$ High: $\geq 120 \text{ mm bpm}$ and increase $\geq 15 \text{ bpm}$

3.6.6.2. Electrocardiograms

ECG parameters (heart rate, RR interval, PR interval, QRS interval, QT interval, QTcB [QT interval corrected using Bazett's method], QTcF [QT interval corrected using Fridericia's method]) will be summarized for each visit during the entire study by enrollment group and overall.

Number and percentage of subjects with QTcB or QTcF parameter values considered PCS occurring at any post-baseline visit will be summarized by enrollment group and overall. Criteria for PCS are presented in [Table 4](#) and will be presented for each criterion. A subject will be counted only once in the highest category for a given parameter based on the largest post-baseline value. The percentages will be calculated relative to the number of subjects with baseline value \leq 450 msec and at least 1 post-baseline assessment in the safety analysis set.

A supportive listing will present all values for a parameter for subjects with at least one PCS value for that parameter.

Table 4: Criteria for Potentially Clinically Significant (PCS) QTcB and QTcF Values

Parameter	Criteria
QTcB and QTcF	> 450 to \leq 480 msec
	> 480 to \leq 500 msec
	> 500 msec
	Change from baseline > 60 msec
	Change from baseline > 60 msec

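### QTc outlier percentages use one baseline cut-off (450 msec or below) for every row and define no numerator, so the >480 and >500 msec rates are either too low or not proper proportions

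*SAP*

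**What the plan says.** SAP 3.6.6.2 plans to report, by enrollment group and overall, the "Number and percentage of subjects with QTcB or QTcF parameter values considered PCS occurring at any post-baseline visit". Table 4 gives the criteria: three mutually exclusive absolute bands (above 450 to 480, above 480 to 500, and above 500 msec) and a change row, "Change from baseline > 60 msec", which appears twice in the text as extracted.

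One denominator serves all of them: "The percentages will be calculated relative to the number of subjects with baseline value" at or below "450 msec and at least 1 post-baseline assessment in the safety analysis set". The counting rule is: "A subject will be counted only once in the highest category for a given parameter based on the largest post-baseline value". A listing follows: "A supportive listing will present all values for a parameter for subjects with at least one PCS value for that parameter".

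Elsewhere the SAP works differently. For vital signs (3.6.6.1): "The percentages will be calculated relative to the number of subjects with non-PCS baseline values with respect to the specific criterion", again with at least one post-baseline assessment. Laboratory values (3.6.5) use the same criterion-specific denominator, and that section also spells out the matching numerator. Section 3.6.6.2 has no such sentence. Protocol 12.6 asks for the number and percentage meeting the criteria at any post-baseline visit and sets no baseline condition. SAP Section 5, on changes from the protocol, mentions only COVID-19.

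**The concern.** A subject with a baseline of 455 msec has not met the >480, >500 or change >60 criterion at baseline, and can newly meet any of them. Under the laboratory and vital-sign rule that subject would be in the denominator for all three. Under the QTc rule the subject is in none.

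ECG parameters are a named endpoint of the safety objective (Protocol Section 4). The study has no control arm under the same restriction, so the absolute percentages are the result. The SAP plans no other QTc outlier table for subjects starting above 450 msec. If such a subject reaches 510 msec, no summary percentage handles the event properly.

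**Working it through.** The plan states no figure to reproduce, so the check compares the text and then illustrates the size on assumed inputs.

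**1. Row by row**

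| Table 4 criterion | Baseline free of that criterion | SAP denominator | Left out though eligible for a new event |
|---|---|---|---|
| Lowest band (>450) | ≤450 | ≤450 | none |
| >480 | ≤480 | ≤450 | 451-480 |
| >500 | ≤500 | ≤450 | 451-500 |
| Change >60 | any | ≤450 | all above 450 |

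**2. Can such subjects be enrolled?** Yes. De Novo exclusion 6 (Protocol 6.2.2) turns on a clinically significant ECG result and gives no QTc limit. The Rollover criteria (6.1.1, 6.2.1) contain no ECG-specific rule.

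**3. The two numerator readings.** Let f be the share with baseline above 450, and let r0 and r1 be the risks of a post-baseline value above 480 for baselines at or below 450 and above 450. All three are assumed.

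- Both restricted: r0.
- Denominator only restricted: [(1−f)·r0 + f·r1] / (1−f).
- Everyone: (1−f)·r0 + f·r1. This equals the criterion-specific rate if nobody is already above 480 at baseline.

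For f = 5%, r0 = 0.5%, r1 = 20%: everyone = 0.95×0.5% + 0.05×20% = 0.475% + 1.000% = 1.475%. Denominator only restricted = 1.475%/0.95 = 1.55%.

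| f | r0 | r1 | Both restricted | Denominator only | Everyone |
|---|---|---|---|---|---|
| 1% | 0.2% | 10% | 0.20% | 0.30% | 0.30% |
| 5% | 0.5% | 20% | 0.50% | 1.55% | 1.475% |
| 10% | 1% | 30% | 1.00% | 4.33% | 3.90% |

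Across f = 1, 3, 5 and 10% with each of these three risk pairs, everyone divided by both restricted runs from 1.29/1.00 = 1.3 to 1.18/0.20 = 5.9. With only the denominator restricted, the percentage is too high by 1/(1−f), at most 1/0.90 = 1.11.

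**4. Simulation with no drug effect.** Normal QTc, one baseline ECG and 10 post-baseline ECGs (the number in the schedule), one million simulated subjects per row. Each cell gives the rate with numerator and denominator both restricted to baseline ≤450, then the rate with the criterion-specific denominator (all subjects for change >60), then the share of events dropped.

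| Mean / between SD / within SD (msec) | Baseline >450 | >480 | >500 | Change >60 |
|---|---|---|---|---|
| 410/15/10 | 1.32% | 0.010% vs 0.039%; 75% | 0.000% vs 0.001%; 100% | 0.011% vs 0.011%; 0.0% |
| 415/18/12 | 5.27% | 0.218% vs 0.759%; 73% | 0.002% vs 0.032%; 93% | 0.194% vs 0.184%; 0.1% |
| 420/18/12 | 8.28% | 0.414% vs 1.456%; 74% | 0.004% vs 0.079%; 95% | 0.196% vs 0.180%; 0.1% |
| 420/20/15 | 11.51% | 1.793% vs 4.136%; 61% | 0.069% vs 0.464%; 87% | 2.068% vs 1.837%; 0.4% |

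The >480 and >500 rows fall clearly. The change row hardly moves, and in three of the four settings the restricted rate is slightly higher, as regression to the mean would suggest.

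**5. How loosely the share is determined.** A normal baseline with mean 400-425 and SD 18-22 msec puts 0.3% to 13% above 450. Take the share of >500 cases dropped as b·hi/[b·hi + (1−b)·lo], with b the share above 450, assumed risk hi of 2-5% above 450 and lo of 0.1-0.2% below. The low end is 0.003×0.02/(0.003×0.02 + 0.997×0.002) = 3%. The high end is 0.13×0.05/(0.13×0.05 + 0.87×0.001) = 88%. That range shows only that the documents do not fix the answer.

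**The case against.** Read literally, 3.6.6.2 restricts only the denominator. A subject going from 455 to 510 msec is then still counted, and the percentage is slightly too high. A reader might infer that the rule plainly removes these subjects and biases the rates low. The documents do not say so, because that needs a numerator restriction nobody has written down. What stands is that neither reading gives a sound percentage.

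A reader might also infer that the highest-risk subjects are removed from the change >60 row. Nothing in the documents shows that a high baseline makes a 60 msec rise likelier, and the simulation suggests little effect. The restriction there simply has no rationale.

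A common baseline below the lowest band is a coherent definition of new onset for exclusive bands counted once per subject. That is fair, and any fix must respect it. It does not explain the departure from the SAP's own rule or supply a summary for subjects starting above 450.

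The subjects are not invisible. The listing keeps all values for anyone with a flagged value, the by-visit summaries include them, and cardiac disorder is an event category of special interest (3.6.4). The study is descriptive, no decision rule rests on QTc, and Protocol 3.2.3.2 reports limited hERG inhibition. These points lower the stakes, but a listing gives no rate and by-visit averages do not show outliers.

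Finally, the repeated change row might suggest a lost second category. That is a guess: it may be a plain duplicate or an artefact of text extraction.

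**Conclusion.** The point holds. One 450 msec baseline cut-off governs all QTc outlier percentages, the numerator is undefined, and for the >480 and >500 rows this conflicts with the SAP's treatment of laboratory values and vital signs. The rates are too low for the safety population if the numerator is restricted too, and are not proper proportions if it is not. For change >60 the restriction is unexplained but probably makes little numerical difference.

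The size is not derivable from the documents. The factor of 1.3 to 6 for >480, and the 61-75% (>480) and 87-100% (>500) of new events dropped in simulation, assume a restricted numerator and invented QTc distributions or risks. Absolute counts may be small: the largest simulated >500 rate, 0.464%, is about 5 per 1000 subjects. Who is affected also depends on the ECG baseline for Rollover Subjects. Protocol 12.3 takes it from the antecedent study, and the SAP does not state one for ECG.

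**What to change.** In SAP 3.6.6.2:

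- State the numerator, and apply the same baseline restriction to numerator and denominator.
- Present >450, >480 and >500 as cumulative rows among subjects with baseline ≤450, ≤480 and ≤500 msec respectively and at least one post-baseline ECG. Alternatively, keep the exclusive bands and add a shift table by baseline QTc category that includes >450.
- Compute the change >60 row among all subjects with a baseline and at least one post-baseline ECG.
- Limit the count-once-in-highest-category rule to exclusive absolute-value bands.
- Check the repeated change row against the source file and correct it if it is really there.

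The cost is SAP wording and slightly more programming, using data already planned. The drawback is that denominators differ by row, so each must be printed.

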3.6.7. Columbia Suicide Severity Rating Scale (C-SSRS)

The C-SSRS is a questionnaire used to measure the presence and intensity of suicidal ideation and behavior. Suicidal behavior and suicidal ideation will be summarized by enrollment group and overall. The proportion of subjects who meet the criterion for each of these categories will be summarized as described in [Table 5](#).

Table 5: C-SSRS Categories for Analysis

Category	C-SSRS Item response is “YES”
Suicidal behavior	Preparatory acts or behavior Aborted attempt Interrupted attempt Actual attempt Complete suicide
Suicidal ideation	Wish to be dead Non-specific active suicidal thoughts Active suicidal ideation with any methods (not plan) without intent to act Active suicidal ideation with some intent to act, without specific plan Active suicidal ideation with specific plan and intent

3.7. Pharmacokinetic Data Analysis

PK analyses will be performed using the PK analysis set. Individual plasma concentrations will be listed by actual sampling times and summarized by nominal sampling times using descriptive

statistics. Plots of individual and mean concentrations over nominal time will also be generated. PK parameters will be calculated using non-compartmental analysis. Parameters will be estimated using actual elapsed time from dosing, and summarized using descriptive statistics. A subject listing of individual PK parameters will be provided.

Non-compartmental analysis will be performed to estimate the PK parameters as data allow. Additionally, PK concentration data obtained from this study will may be combined with data from other studies to develop a population PK model, which will be reported separately.

The PK parameters to be calculated includes, but is not limited to:

- C_{\max} : Maximum observed concentration
- t_{\max} : Time to reach C_{\max}
- AUC_{last} : Area under the plasma concentration versus time curve calculated using the trapezoidal method from time zero to the last observed concentration above the lower limit of quantification.

3.8. Statistical Considerations for COVID-19

Due to the Coronavirus Disease 2019 (COVID-19) public health emergency, many data collection challenges arose in this study. However, additional efforts were made to collect more data related to COVID-19, including but not limited to protocol deviations, AEs for COVID-19, COVID-19 testing and vaccine for COVID-19, concomitant medication to treat COVID-19 AEs and vaccines to prevent COVID-19, and treatment and study discontinuation due to COVID-19 etc.

The impact of COVID-19 will be evaluated for the safety population. Data for subjects who discontinued the study due to COVID-19 will be summarized with the reason for discontinuation in the listing. An overview table, including the number of subjects with TEAEs, serious AEs (SAEs) related to COVID-19, will be provided by enrollment group and overall. All AEs related to COVID-19 will be included in the listings. COVID-19 related concomitant medication data will be summarized and included in the listings. Major protocol deviations related to COVID-19 will be provided in the listings. The protocol deviations log may be used to summarize the impact of COVID-19 in this study.

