### 5.2. Study Duration for Subjects

Subjects will enter into the study in one of two ways:

De Novo Subjects: Those who have not participated in any prior eligible study of ALKS 8700.

Rollover Subjects: Those who have completed the treatment period for any prior eligible study of ALKS 8700.

For De Novo Subjects, the study duration is expected to be up to 102 weeks, which includes up to 4 weeks for screening, a 96-week open-label treatment period, and a 2-week follow-up period.

De Novo Subjects will be initially evaluated for eligibility at screening (Visit 1) that may last up to 28 days (4 weeks) prior to Visit 2. For Rollover Subjects, Visit 2 will be the first visit of the study and there will not be a separate screening visit. For these subjects, Visit 2 of this study will occur at the time of or within 7 days of the subject's end of treatment visit in the antecedent study. Completed assessments taken at the end of treatment visit of the antecedent study will be carried forward and do not need to be repeated at Visit 2 of this study unless otherwise specified in the schedule of assessments. At Visit 2, all eligible, consenting subjects will begin open-label treatment. Any subject not currently receiving ALKS 8700 or DMF will initiate treatment with ALKS 8700 231 mg BID on Day 1 through Day 7 followed by 462 mg BID from Day 8 onwards. For those subjects already receiving ALKS 8700 or DMF prior to Day 1, the initial ALKS 8700 dose will be 462 mg BID starting from Day 1.

Dosing is described in detail in [Section 7.1](#). From Day 8 onwards, all participating subjects will take ALKS 8700 462 mg BID, with allowable dose reduction for tolerability as described in [Section 7.2](#).

Study staff will administer the first dose of ALKS 8700 at Visit 2 (Day 1). From that point on during the treatment period, according to the schedule of assessments as shown in [Table 1](#), the staff will dispense ALKS 8700 for subjects' self-administration. Subjects will be instructed to take study treatment with or without food. However, subjects will be instructed to avoid taking study treatment with a high-fat, high-calorie meal.

CONFIDENTIAL

The information contained herein may not be used, disclosed, or published without the written consent of Biogen MA Inc.

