**8. Change: Update estimated LSLV**

**Description of Change:** The estimated date of last subject's last visit was updated from Q4 2019 to Q3 2021.

**Rationale for Change:** A302 German subjects will be rolled over into A301 (2 year) study which will push back the A301 LPLV in Q4 2020 or somewhere in 2021. Q3 2021 was agreed by team.

**Sections Impacted:** [Section 2](#): Synopsis (Study Period)

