3. DATA ANALYSES

3.1. Study Population

The study population, defined as all enrolled subjects who receive at least one dose of ALKS 8700, will be divided into three enrollment groups for summarizing safety and efficacy data:

1. De Novo Subjects
2. Rollover Subjects who were in ALKS8700 treatment group
3. Rollover Subjects who were in DMF treatment group

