3.1.1. Definitions of Analysis Populations (Analysis Sets)

3.1.1.1. Safety Population

The safety analysis set, defined as all enrolled subjects who receive at least one dose of ALKS 8700, will be used in the safety analyses.

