7. GENERAL STATISTICAL METHODOLOGY

In general, summary statistics (n, mean, SD, median, minimum, and maximum for continuous variables, and number and percentage of subjects in each category for categorical variables) will be provided by treatment group. All summary tables will be based on observed data, and missing values will not be imputed unless otherwise indicated. Measurements collected from unscheduled visits or repeated assessments will not be included in the by-visit summary tables or figures, but will be included in the derivation of the last post-baseline value during treatment, the analyses for the potentially clinically significant (PCS) post-baseline values, and subject listings. Source data for the summary tables and statistical analyses will be presented as subject data listings.

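### COVID-19 adverse events are summarized on everyone ever dosed, so their percentages understate the risk among subjects on study during the pandemic and can differ between De Novo and rollover subjects through entry date alone

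*SAP*

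**What the plan says.** SAP 3.8 sets the base for all COVID-19 summaries: "The impact of COVID-19 will be evaluated for the safety population". SAP 3.1.1.1 makes that set "defined as all enrolled subjects who receive at least one dose of ALKS 8700, will be used in the safety analyses", with no calendar limit. The adverse event display is described so: "An overview table, including the number of subjects with TEAEs, serious AEs (SAEs) related to COVID-19, will be provided by enrollment group and overall". The groups come from SAP 3.1, where subjects "will be divided into three enrollment groups for summarizing safety and efficacy data": De Novo, rollover from ALKS 8700 and rollover from DMF.

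SAP 3.8 refers to numbers of subjects. Percentages follow from SAP 7, which prescribes "number and percentage of subjects in each category for categorical variables". The main adverse event overview in SAP 3.6.2 is worded in the same way as the COVID-19 one.

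SAP 3.8 also says that "additional efforts were made to collect more data related to COVID-19". No section gives a COVID-19 start date, a subset of subjects on study after it, or person-time from it.

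The only calendar evidence is in the amendment summary attached to the protocol. There, under change 8, the estimated date of the last subject's "last visit was updated from Q4 2019 to Q3 2021", to take in German rollovers from Study A302. Change 2 of the same amendment raised the planned size from 800 to about 1000, also because of A302 rollovers.

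**The concern.** COVID-19 could be recorded only in the later calendar part of this study. Follow-up per subject is fixed at "a 96-week open-label treatment period, and a 2-week follow-up period", and under Protocol 11.3.1 routine adverse event collection ends at Visit 16. Anyone who had reached Visit 16 before the pandemic could not contribute a COVID-19 event, yet is counted in the denominator.

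Two misreadings could follow. The overall percentage could be taken as the frequency of COVID-19 in subjects on ALKS 8700 during the pandemic, which it understates. A gap between De Novo and rollover subjects could be taken as an effect of prior treatment when it reflects entry date. Readers will look at these figures because SAP 3.6.4 makes lymphopenia, serious infections and opportunistic infections events of special interest.

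**Working it through.** The documents give no COVID-19 rate and no count of subjects on study in the era, so there is no planned figure to reproduce. Two checks apply.

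**1. Who could have an event?** Protocol Table 1 puts Visit 2 on Day 1 and Visit 16 on Day 687, so a completer is followed for 686 days. Entry date = last-visit date minus 686 days.

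| Last visit | Latest entry for a completer |
|---|---|
| Q4 2019 (1 Oct to 31 Dec 2019) | 14 Nov 2017 to 13 Feb 2018 |
| Q3 2021 (1 Jul to 30 Sep 2021) | 15 Aug to 14 Nov 2019 |

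The SAP gives no era start. If it is assumed to lie between 1 January and 1 April 2020, a completer must have entered on or after a date between 14 February and 16 May 2018 to be in adverse event collection then. A completer who fitted the earlier Q4 2019 timeline was therefore out before the era under any of these dates.

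**2. How much does this dilute the percentage?** Let N be the number dosed in a group, f the share on study at some time in the era, and r the risk among those subjects. Subjects with an event number N × f × r, so

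reported percentage = (N × f × r) / N = f × r.

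On an on-study base the denominator is N × f and the result is r. For r = 5% (assumed):

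| f | Safety-population base | On-study base |
|---|---|---|
| 0.10 | 0.5% | 5% |
| 0.25 | 1.25% | 5% |
| 0.50 | 2.5% | 5% |
| 0.75 | 3.75% | 5% |

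With equal r in two groups, the ratio of reported percentages is the ratio of their f values. With f = 0.25 and 0.50 the groups show 1.25% and 2.5%, a ratio of 2. With equal f they do not differ.

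**A range for f, all subjects pooled.** Assumptions: uniform entry from 1 January 2016, 2017 or 2018 to 14 November 2019; 686 days of follow-up; exponential dropout of 0-25% over that time; era starting 31 January or 11 March 2020.

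| Assumed accrual start | Subjects with time in the era | Patient-time in the era | 5% risk reported as |
|---|---|---|---|
| January 2016 | 34-43% | 16-19% | 1.7-2.2% |
| January 2017 | 46-58% | 21-26% | 2.3-2.9% |
| January 2018 | 70-89% | 32-40% | 3.5-4.5% |

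As a hand check for a 2016 start, no dropout and 31 January 2020: entry must be on or after 16 March 2018, and 608 of the 1413 accrual days qualify, so f = 608/1413 = 0.43.

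This range shows how the result depends on accrual; it does not bound it. No f can be calculated for each enrollment group, because entry dates by group are not given.

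**The case against.** The strongest reply is that SAP 3.8 asks how far COVID-19 affected this trial, through deviations, discontinuations, adverse events and medication. For that question the whole safety population is a proper base, and it matches the other adverse event tables. The SAP nowhere claims to estimate COVID-19 incidence under the drug. This stands, and it is why the safety-population figures should be kept.

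A second reply is that SAP 3.8 promises counts, and counts are not diluted. This does not carry far. SAP 7 calls for number and percentage, and the main overview in SAP 3.6.2 uses the same wording. Bare counts by group also cannot be interpreted without the number on study in the era, which no described output gives. The mock tables are a separate document, so the printed denominator cannot be confirmed.

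A third reply is that little depends on this. The table is descriptive, SAP 3.8 specifies no test or comparison between groups, and all COVID-19 events are listed. SAP 3.6.4 presents events of special interest by preferred term, which already separates COVID-19 from other infections. This stands and limits the point to a minor one.

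On the other side, the SAP already restricts denominators to subjects who can have the event elsewhere: laboratory and vital-sign percentages use subjects with an unremarkable baseline (3.6.5, 3.6.6.1), and QTc percentages use those at or below 450 msec at baseline (3.6.6.2). An on-study base for COVID-19 would follow the same logic.

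**Conclusion.** The point holds as a minor one. On the safety population the COVID-19 percentage is f × r, which is below the risk among subjects on study in the era whenever f is less than 1. De Novo and rollover percentages can differ through entry date alone. Under the accrual assumptions above, a 5% risk would be reported as about 1.7-4.5%; at the upper end the dilution is negligible.

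Three stronger readings are tempting, and the documents do not support them.

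- **Most De Novo subjects had left, so their figure would be near zero.** The amendment summary makes later entry plausible for some A302 rollovers. It gives estimated dates, not actual ones, and no De Novo entry dates or group sizes.
- **The two rollover groups would differ from each other.** SAP 3.2 ties both to A302, and nothing suggests different calendar coverage.
- **The drug's infection profile would be misreported.** Event counts are unaffected and every COVID-19 event is listed. No safety conclusion is overturned.

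**What to change.** In SAP 3.8:

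- State one fixed COVID-19 era start date.
- Keep the safety-population counts as the measure of impact on the trial.
- Add, per enrollment group and overall, the number of safety-population subjects on study on or after that date and their patient-years from it.
- Give COVID-19 TEAEs and SAEs as percentages of that number and as rates per 100 patient-years from that date.

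Showing the serious-infection rows with and without COVID-19 terms is optional, given the preferred-term rows.

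The cost is one date, one subject flag and a few added rows, all from data already collected. The downside is smaller denominators and somewhat higher percentages.
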